## 8 Data handling and data management

#### 8.1 Source documents and other records maintained by the investigator

It is the treating investigators' obligation to assure documentation of all relevant data in the subject's source record, such as the informed consent process and date of enrollment into the clinical investigation, medical / aesthetic history, prior and concomitant treatments, visit dates, clinical observations including AEs (including reporting and follow-up of AEs), results of all assessments, information related to medical device application, and the date of subject's exit from the investigation, including the reason.

Any form completed by the subject (including the eDiary) is also considered as a source document and must be kept in the subject's source record. The location of the source documents shall be documented.

In addition, the investigator must maintain all other essential documents pertaining to the clinical investigation as defined by GCP and applicable regulatory requirements.

#### 8.2 Case report forms

A CRF will be completed for each subject who signed an ICF. Data on each subject screened / randomized in the investigation will be recorded pseudonymously in the web-based validated electronic CRF (eCRF), which is designed to accommodate the specific features of the clinical investigation design

and complies with regulatory requirements on electronic data transfer. The system is compliant with 21 CFR Part 11 regulation.

Only the treating investigator and their authorized designees are allowed to make entries in the eCRF. This will be regulated by appropriate read and write access. Completed eCRFs will be electronically signed by the treating investigator or their authorized designee.

All site personnel, sponsor and CRO personnel seeking access must go through a thorough training process before they are granted access. Furthermore, all study personnel will be instructed how to fill in the CRFs. The CRF Completion Guide will provide additional information additional instructions for CRF documentation.

Data required according to this protocol are to be recorded on the eCRFs as soon as possible. The Principal Investigator must assure that all data are entered completely, and accurately according to the CRF Completion Guide, and is ultimately responsible for conformance of CRF entries with source data.

Completed eCRFs will be electronically signed by the Principal Investigator or their authorized designee (only treating investigators).

Any subsequent change, deletion or addition will be recorded by an audit trail system, which will require re-signing of the CRF.

#### Data recorded from screening failures

The minimum data to be recorded for screening failures in the subject's source records and in the CRF will be given in the CRF Completion Guide.

#### 8.3 Data management procedures

All data management activities will be conducted by the sponsor's representative following their standard operating procedures. They will build the database and handle the data cleaning process, including logical checks, medical checks, and query process. Subject data necessary for analysis and reporting will be transmitted into a validated database. Details on data handling and data cleaning will be described in the Data Management Plan (DMP).

# Procedures for verification, validation and securing of electronic clinical data management systems (CDMS)

The study specific eCRF and ePRO are implemented on a validated CDMS. The validation requirement for the study specific eCRF and ePRO is served by the following components:

- The data entry screen testing and edit check testing serve as evidence of a database that performs for its intended use of capturing and cleaning of clinical data (user acceptance testing).
- The validation of electronic clinical data management systems will be done according to the regulatory requirements and respective SOPs.
- Any validation is performed on a self-contained development and test environment of the CDMS, eCRF and other applications. These environments are identical to the productive version. The test data are not mixed with data of other environments.

#### Procedures for Data Cleaning

Computerized validated check programs on completeness, correctness, plausibility (such as range checks, cross-checks, edit checks) will verify the data according to the listing of all planned programmed data integrity checks, the Data Cleaning Plan (DCP). All identified discrepancies will be queried and addressed to the respective site staff. The investigator or their authorized designee must carefully answer any query issued by Data Management.

Coding of concomitant diseases, adverse events and concomitant treatments will be coded using the MedDRA system and the WHO Drug Global. Device deficiencies will be coded using International Medical Device Regulators Forum (IMDRF) Annex A.

Upon completion of data collection and all data cleaning activities, i.e., when the database is considered complete and accurate, it is considered soft locked and reviewed by the sponsor together with the clinical investigation team during the DRM.

The database will be hard locked after sponsor's approval. All changes will be tracked by audit trail. Once hard locked the final clean datasets will be exported for final statistical analysis.

#### Interim analysis

An interim analysis (IA) assessing the safety and effectiveness will be performed after all subjects have completed the follow-up visit at Week 48 after last injection of the initial treatment phase (Visit 9 (SV1)). For the interim analysis the database will be cleaned and a data base lock prior to export for data analysis will be done.

## 8.4 Data retention

The investigator shall retain all clinical investigation records (including all individual subject-related documents (e.g., subject's questionnaires, eDiary and ICF), device-related records, investigation-related correspondence, and all other documents contained in the Investigator's Site File) during the clinical investigation and for the period required by the applicable regulatory requirements, or the time period specified in the contract between the sponsor and the investigator, whichever is longer.

In any case, the investigator must contact the sponsor in writing prior to destruction of any records pertaining to the clinical investigation, to get confirmation that these no longer need to be retained. In addition, the sponsor should be informed in writing if the investigator plans to leave the site or chooses to store the records at a different physical address than the site address, to ensure traceability of the records and appropriate arrangements for the transfer of custody.

The source records of subjects taking part in the investigation must be retained in accordance with local legislation and the maximum period permitted by the hospital, institution or private practice.

## 8.5 Report of the clinical investigation (CIR)

Following completion of the clinical investigation, the results will be evaluated, and the Clinical Investigation Report (CIR) will be generated. Based on the interim analysis results an interim Clinical Investigation Report (iCIR) will be generated. Both, the iCIR and CIR will include a summary of all available data, statistical measures, tabulated results, graphical results (if any), and interpretations. A complete list of all adverse events will be enclosed. The reports will be submitted to relevant authorities as appropriate, within the timeframes defined per national regulation and/or to the IRB/EC as applicable.

# 9 Amendments to the clinical investigation plan (CIP)

Any change of this CIP can only be made in form of a written amendment. Such amendment must be discussed, agreed upon and signed by the sponsor, the Coordinating Investigator and the Principal Investigators before implementation.

Any amendment which may affect the validity of the data or information resulting from original CIP, the risk-benefit ratio for the subject, the scientific soundness of the investigation, change of the principal investigator or the rights, safety or welfare of subjects taking part in the investigation will also have to be reviewed and approved by the IRB/EC and regulatory authorities, if applicable, prior to implementation.

Amendments with impact on procedures to be performed, risk-benefit ratio for the subject and/or the well-being of the subjects require additional informed consent, which must be given in writing by all subjects enrolled in the clinical investigation who are affected by the amendment.

# 10 Deviations from the clinical investigation plan

A CIP deviation is a failure to follow, intentionally or unintentionally, the requirements of the CIP. As required by national regulation or guidelines, requests for deviations and reports of deviations will be provided to the IRB/EC if the deviation affects subject's rights, safety and well-being, or the scientific integrity of the clinical investigation.

Under emergency circumstances, deviations from the CIP may proceed without prior approval by the sponsor and favourable opinion of the IRB/EC if the rights, safety and well-being of human subjects need to be protected. Such deviations will - however - be documented and reported to the sponsor and the IRB/EC as soon as possible in accordance with national regulations. **No waivers to the CIP will be granted by the sponsor.** 

The investigator must maintain accurate, complete and current records of any deviation from the CIP, including the date and reason for each deviation.

The investigator shall notify the sponsor and the reviewing IRB (as applicable) of any deviation from the CIP made to protect the life or physical well-being of a subject in emergency as soon as possible, but in no event later than five working days after the emergency occurred.

All CIP deviations will be listed and their impact on evaluability of respective subjects will be discussed during the interim DRM and during DRM prior to the hard data base lock.

## **11** Device accountability

The device accountability is described in section 6.2.6.

## **12** Statements of compliance

This clinical investigation will be conducted in compliance with this CIP and the following standards and regulatory requirements:

- International Standard ISO 14155:2020 Clinical investigation of medical devices for human subjects
   Good Clinical Practice (GCP)
- Declaration of Helsinki, in its currently adopted version
- Applicable national medical device laws / regulations.

By acting in accordance with this CIP, the investigators and the investigation site personnel fulfil the requirements of ISO 14155:2020.

The clinical investigation will not commence until a favorable opinion from the respective EC has been received. All additional requirements imposed by the IRB/EC will be followed. A prior regulatory approval will also be sought, if required by national regulations.

Insurance coverage for damages emerging from the clinical investigation will be provided according to applicable legal requirements.

## **13** Informed consent process

The informed consent form (ICF) must be notified to, or approved by, the IRB/EC and regulatory authorities, if required by local regulations.

Written informed consent must be obtained from each subject prior to initiation of any of the investigation-specific procedures.

The investigator or their authorized designee must give each subject complete and adequate verbal and written information about the investigation. The investigator must ensure that the subject is fully informed about the aims, procedures, potential risks, any discomforts, and expected benefits of the clinical investigation. It must be emphasized that participation is voluntary and that the subject has the right to withdraw from the clinical investigation at any time without any justification and without prejudice. They also must be informed that the quality of their medical care will not be adversely affected if they decline to participate in the investigation or in case of subsequent consent withdrawal. Before consenting, the subject must be left with ample time to consider and ask questions.

The subject must then sign and date the Informed Consent Form (ICF) prior to the conduct of any investigation-related procedures. The consent taker (the investigator or, according to local laws, their designee) must sign and date the ICF as well.

The investigator will document the entire informed consent process in the subject's source record (e.g., date (and time as applicable) of informed consent / signature, who has informed the subject, and that s/he has informed the subject, that the subject had ample time to consider, that the subject and the investigator have signed the ICF). In addition, the date (and time as applicable) of informed consent / signature will be recorded in the eCRF.

A signed and dated copy of the ICF will be given to the subject for their records. The other copy of the signed and dated ICF will remain in the Investigator's Site File.

If subject's participation in the investigation or decision to participate in the investigation is or may be affected by an amendment to the CIP (e.g., a change in any procedure) or any other important new information, which may relate to the subject's willingness to continue participation in the clinical investigation, the ICF must be amended accordingly, and the subject must sign the amended ICF indicating that they re-consent to participate in the clinical investigation.

## 14 Adverse events, adverse device effects and device deficiencies

## 14.1 Definitions

Adverse Event (AE) is any untoward medical occurrence, unintended disease or injury or untoward clinical sign (including abnormal laboratory findings) in subjects, users or other persons, whether or not related to the device and whether anticipated or unanticipated. This definition includes events related to the test device, the comparator device and events related to the procedures involved.

• For subjects taking part in the clinical investigation this definition includes events related to the device and procedures involved, as well as pregnancy in females.

**Note 1:** The event of pregnancy meets the SAE criterion if it results in a spontaneous abortion or a congenital anomaly or it is suspected that the device or study procedure interacted with the contraceptive method and has led to pregnancy. Pregnancy is not considered an (S)AE *per se*.

**Note 2:** Injection site reactions the subject is specifically asked about in the subject diary (see section 6.4.19) will **not** be collected as AEs during the first four weeks (28 days) after each treatment (i.e., 4 weeks after baseline and repeat-treatment, respectively, and 6 weeks in case of touch-up treatment). Any injection site reactions that continue for more than 28 days post-administration will be assessed and documented as AEs by the treating investigator as described in the sections below.

**Note 3:** Injection site reactions the subject is **not** specifically asked about in the subject diary (i.e., 'Other' symptoms at the injection site not listed in section 6.4.19) and that are **not** synonymous to one of the pre-defined injection site reactions will be assessed and documented as AEs by the treating investigator as described in the sections below.

• For users or other persons this definition is restricted to events related to the use of both devices (test device or comparator device).

Adverse Device Effect (ADE) is an AE related to the use of the device.

This includes This definition includes

- AEs resulting from insufficient or inadequate instructions for use, deployment, implantation, installation, or operation, or any malfunction of the device
- any event resulting from use error or from intentional misuse of the investigational medical device.
- the comparator device

Serious Adverse Event (SAE) is an AE that led to any of the following conditions:

- Death;
- Serious deterioration in the health of the subject, users, or other persons as defined by one or more of the following:

- o A life-threatening illness or injury, or
- o A permanent impairment of a body structure or a body function including chronic diseases, or
- o In-subject or prolonged hospitalization, or
- Medical or surgical intervention to prevent life-threatening illness or injury or permanent impairment to a body structure or a body function
- Fetal distress, fetal death, a congenital abnormality, or birth defect including physical or mental impairment.

Planned hospitalization for pre-existing condition or a procedure required by the CIP without a serious deterioration in health is not considered a SAE.

**Serious Adverse Device Effect (SADE)** is an ADE that has resulted in any of the consequences characteristic of an SAE.

**Serious health threat** is a signal from any adverse event or device deficiency that indicates an imminent risk of death or a serious deterioration in the health in subjects, users or other persons, and that requires prompt remedial action for other subjects, users or other persons. This would include events that are of significant and unexpected nature such that they become alarming as a potential serious health hazard or possibility of multiple deaths occurring at short intervals (according to ISO 14155).

Adverse Events of Special Interest (AESI) (serious or non-serious) is one of scientific and medical concern specific to the sponsor's product or program, for which ongoing monitoring and rapid communication by the investigator to the sponsor could be appropriate. Such events may require further investigation in order to characterize and understand them. Depending on the nature of the event, rapid communication by the sponsor to other parties may also be needed (see section 14.5).

For this clinical investigation, AEs of special interest are defined as embolic events, with possible, probable, or causal relationship to an intravascular injection of the device, as:

- Changes in vision (i.e. loss of vision, blurriness, double vision, pain in or around your eye, blindness, blind spots, problems moving the eyes)
- Skin changing color around the eyelids or around the site of injection
- Other embolic phenomenons, e.g., stroke, skin necrosis, or impending necrosis

#### Unanticipated (Serious) Adverse Device Effect:

- Unanticipated Serious Adverse Device Effect (USADE) is defined as a SADE which by its nature, incidence, severity (intensity) or outcome has not been identified in the current risk assessment and the current version of the Investigator's brochure (IB) (adapted according to ISO 14155)
- For USA only: Unanticipated adverse device effect (UADE) is defined as any serious adverse effect on health or safety or any life-threatening problem or death caused by, or associated with, a device, if that effect, problem, or death was not previously identified in nature, severity (intensity), or degree of incidence in the investigational plan or application (including a supplementary plan or application), or any other unanticipated serious problem associated with a device that relates to the rights, safety, or welfare of subjects" (according to investigational device exemption (IDE) regulations / 21 CFR 812.3(s)).

**Device deficiency** is an inadequacy of a medical device with respect to its identity, quality, durability, reliability, usability, safety or performance. Device deficiencies include malfunctions, use errors, and inadequacy in the information supplied by the manufacturer including labelling. This definition includes device deficiencies related to the test device or the comparator device.

**Device deficiency that might have led to a SAE** if a) suitable action had not been taken, or b) intervention had not been made, or c) if circumstances had been less fortunate, is classified as a special type of deficiency and is handled under the SAE reporting system.

## 14.2 Method of detecting AEs

AEs will be detected by observation and by asking the subject about the occurrence of AEs. Care should be taken not to introduce bias when eliciting AE information from the subject. Open-ended and non-leading verbal questioning is the preferred method and appropriate questions include:

- *"How are you feeling?"*
- "Have you had any medical problems since your last visit/contact?"
- "Have you taken any new medication since your last visit/contact?"

In order to identify potential AEs post-administration of device safety evaluation 15 minutes after the device administration needs to take place (see section 6.4.20).

All SOI(s) documented by the subject in the eDiary (see section 6.4.19) must be verified by the investigator either by specific questioning of the subject and/or physical examination or visual inspection. SOI(s) *considered clinically significant* should be documented as AE(SI)(s). SOIs that turn out to be not clinically significant (see section 20.5.1 for examples) due to any reason are not considered as AE(SI) and need not to be documented as AE(SI) in the eCRF. However, the investigator should add a statement in the subject's source records why the SOI was not considered clinically significant, i.e., as AE(SI).

All AESIs (serious and non-serious, see section 14.1 for definition) and any other embolic event (regardless of seriousness and / or relationship to device or procedure) resulting from SOI assessment have to be reported by the investigator to the sponsor's representative within 24 hours of awareness of the event (see section 14.5).

In addition, the subjects will be instructed to immediately contact the investigator/investigation site in case of occurrence of any untoward event between visits and an unscheduled visit will be performed (see section 6.5.17). Throughout the entire investigation the investigator should also verify results of all assessments with respect to possible AEs.

## 14.3 AE/SAE documentation

For each AE the following must be reported:

- Description of the event (event term)
- Seriousness
- Start date
- Intensity
- Action taken with subject (none, medical and/or surgical / non-pharmaceutical procedure)
- Action taken with device (none [no action taken], device withdrawn [no touch-up treatment(s) / repeat-treatment due to AE], device interrupted [touch-up treatment(s) / repeat-treatment later than required by study design due to AE or injection interrupted due to AE during treatment session])
- Outcome
- End date (if applicable)
- The relationship to the device and procedure, respectively

The information will be documented in subject's source record and in the eCRF.

Each AE and any new information concerning these events has to be documented, even if the investigator feels that it is not connected with the device or procedure.

The AE will be described in precise, standard medical terminology. The investigator will attempt to establish a diagnosis of the event based on signs, symptoms, and/or other clinical information (including affected body site(s)). In such cases, the diagnosis will be documented as the AE and not the individual

signs/symptoms. In case of any injection site reaction the exact location (e.g., upper or lower lips) should be clearly noted.

Each AE should be reported separately. The investigator will record all AEs in subject's (medical) record and on the "Adverse Events" page of the eCRF. For SAEs, the "Serious Adverse Event Reporting Form" must also be completed. Complete description of all AEs should be also available in source documents of the subject.

Adverse events will be documented beginning after provision of informed consent until the last visit of the subject. The follow-up period will be prolonged outside the investigation, if a related AE is ongoing and not stabilized after 24 weeks after last injection of the repeat-treatment phase (see section 14.6 for details).

AEs initially observed during or after baseline treatment are defined as treatment-emergent AEs (TEAEs). AEs occurring after informed consent but before baseline treatment will be defined as non-TEAEs. Any medical condition that is present prior to day of screening should be considered as medical history (i.e., concomitant disease) and not recorded as an AE. If such condition, however, deteriorates after the device administration, at any time during the investigation, it should be reported as an AE.

If the intensity or seriousness of an AE changes over time, the most severe intensity or seriousness of the AE will be recorded and included in the analysis. No separate AEs will be recorded for each intensity or seriousness level.

Changes in causality assessment should also be clearly documented. AEs related to the device as well as to investigation procedure must be documented. Any medication and non-pharmacological procedure necessary for the therapy of an AE must be recorded on the respective page of the eCRF.

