# 5.3.4 Safety endpoints

The safety of the investigational device will be evaluated by treatment group including cross-over group (in repeat-treatment) and by treatment phase using the following endpoints:

- Occurrence and frequency of adverse events during the entire study period including repeattreatment phase (long-term safety). Symptoms of interest will be recorded in subject diary during the first 4 weeks (28 days) after each treatment (i.e., either 4 weeks after baseline and repeattreatment, respectively, and 6 weeks in case of touch-up treatment) and documented as AE by investigator.
- Injection site reactions as recorded in the subject diaries during the first 4 weeks (28 days) after each treatment (i.e., either 4 weeks after baseline and repeat-treatment, respectively, and 6 weeks in case of touch-up treatment). Injection site reactions will be assessed overall and for each side of the midface (i.e., left and right side separately).

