#### 6.4.9 Neurological examination (F.A.S.T)

The "F.A.S.T" examination is a basic neurological examination that will be performed by treating investigator (or authorized designee) according the instructions given in Table 19 for all subjects who show signs of ophthalmic complications due to filler injection.[27, 28]

Symptom	Instructions for Use
F - Facial	Ask the patient to smile or show teeth. Look for lack of symmetry.
drooping	Does one side of the face droop or is it numb?
	Is the person's smile uneven?
A - Arm weakness	Lift the patient's arms together to 90° if sitting; 45° if supine and ask him/her to hold the position for 5 seconds then let go. Or ask the person to raise both arms.
	Is one arm weak or numb?
	Does one arm drift downward or fall rapidly?
S - Speech	Look for disturbance of speech.
difficulty	Look for slurred speech.
	Look for word-finding difficulties. This can be confirmed by asking the patient to name commonplace objects that may be nearby, such as a cup, chair table, keys, pen.
	If there is a severe visual disturbance, place an object in the patient's hand and ask him/her to name it.
T - Time	Time to call emergency services

Table 19. F.A.S.T. Warning Signs and Instructions for Use (adapted per [27, 28])

More ways to spot a stroke [27]

- Sudden weakness or numbness of face, arm or leg, especially on one side.
- Sudden confusion, trouble speaking or understanding.
- Sudden trouble seeing in one or both eyes.
- Sudden trouble walking, dizziness, loss of balance or coordination.
- Sudden, severe headache with no known cause.

If any of the symptoms above are showing, time is of the essence; call the emergency services and redirect the patient to the hospital / acute stroke unit immediately.

Any clinically significant change compared to prior of each device application will be recorded as AE according to section 14 in the subject's source record and the eCRF. Special focus must be on the AESIs as defined in section 14.1.

If any of the above changes occurs at any assessment, the treating investigator must refer the subject to a neurologist to evaluate if the result is related to a vascular injection of the dermal filler.

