## 7.3.8 Safety endpoints

AEs will be encoded using the MedDRA thesaurus in the most recent version available at the beginning of the study. This version will be used throughout the entire study. Updates of the MedDRA thesaurus will not be applied afterwards.

All AEs will be listed by subject, user or other persons, date and time since last treatment. Incidence of AEs will be summarized by preferred term (PT) and system organ class (SOC), and also by intensity, duration causal relationship to the device or procedure, and seriousness.

The frequency and occurrence rate, maximum intensity, overall duration, and seriousness of injection site reactions within four weeks (28 days) after baseline treatment, after repeat-treatment injection, respectively, and 6 weeks in case of touch-up treatment, will be summarized by device.

The number and percentage of subjects, user or other persons with at least one device deficiency will be summarized. Details concerning device deficiencies will be listed by treatment group and subject.

Urine pregnancy tests will be listed only.

The data will be presented for the SAF using frequency tables.

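### The one-record rule for adverse events leaves no date for worsening after the repeat injection, so that worsening cannot be attributed to the repeat phase or the cross-over group

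*Protocol*

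**What the plan says.** Section 14.3 lists the fields for each AE. They include one start date, one intensity, one seriousness, an end date and the relationship to device and procedure. There is no date of worsening. If an AE changes over time, "the most severe intensity or seriousness of the AE will be recorded and included in the analysis", and then: "No separate AEs will be recorded for each intensity or seriousness level". On causality, "Changes in causality assessment should also be clearly documented".

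The same section defines treatment emergence by first observation: "AEs initially observed during or after baseline treatment are defined as treatment-emergent AEs (TEAEs". AEs that arise between consent and baseline treatment are called non-treatment-emergent. The Glossary entry for Adverse Event, in its study-specific addition, also counts worsening of pre-existing AEs as treatment-emergent.

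Section 5.3.4 says that safety is "evaluated by treatment group including cross-over group (in repeat-treatment) and by treatment phase". Section 5.2.3 names safety after repeat treatment and safety in cross-over use as objectives. The repeat injection is the test device for everyone, including former comparator subjects (section 6.1.1). Section 7.3.8 plans this listing: "All AEs will be listed by subject, user or other persons, date and time since last treatment". It also plans incidence summaries by intensity, causality and seriousness.

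**The concern.** The repeat phase exists largely to show what a test-device injection does in subjects who already carry filler, some of it the comparator. That requires events after RT1 to be separable from events before it. For a new event the start date does this. For an event already open at RT1, the information of interest is the change after the injection, and the recording rule stores that change only as a higher grade on the old record. Any table of repeat-phase events by intensity or seriousness that relies on start date would miss it. The planned time since last treatment would also describe the original onset and not the worsening.

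**Working it through.** The plan gives no figure to reproduce. The check sets the provisions side by side, followed by arithmetic on scale.

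**Step 1: follow the rule for one subject.** Take a hypothetical comparator subject with a mild AE that starts between Visit 8 and Visit 9, is judged not related, is still open at RT1 and becomes severe after the test-device injection.

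| Item | What the section 14.3 record holds | What sections 5.2.3 and 5.3.4 need |
|---|---|---|
| Onset | Start date before Visit 9 | Date on which it became severe, after RT1 |
| Intensity | Severe (worst ever) | Mild before RT1, severe after |
| Causality | One assessment, with changes documented | Relationship of the worsening to the repeat injection |
| Second record | Not allowed | Needed, or a dated entry in its place |

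The grade belongs to one phase and the only onset date to another.

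**Step 2: who can have an open AE at RT1?** Repeat exclusion 2 (section 6.3.5.2) bars subjects with a related AE that occurred in the initial treatment phase and is ongoing. Related includes possible. Exclusions 1 and 3 add related serious AEs, AEs of special interest, clinically significant visual changes and other serious medical conditions. Two groups remain:
- subjects with open AEs judged not related;
- read literally, subjects with related AEs that start between Visit 9 and RT1. The Glossary ends the initial phase at Visit 9 (SV1), so exclusion 2 does not name them. Screening visits run to 12 weeks after Visit 9, and Table 3 allows RT1 up to 14 days after a screening visit.

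**Step 3: the two definitions of treatment-emergent.** Take an AE that starts after consent and worsens after the first injection. Under the Glossary it is treatment-emergent. Under section 14.3 it is not, because it was first observed before treatment, and the one-record rule allows no second record that could qualify. This conflict needs no assumption about the SAP.

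**Step 4: scale.** Inputs: about 300 repeat-treated subjects and 324:162 allocation (section 6.3.1).
- Cross-over subjects if both arms qualify in proportion: 300 × 162/486 = 100. One event is 1/100 = 1.0 percentage point.
- Assumed comparator share of 25%: 300 × 0.25 = 75, and 1/75 = 1.3 points.
- Assumed comparator share of 50%: 300 × 0.50 = 150, and 1/150 = 0.7 points.

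The number of subjects with an AE open at RT1, and the fraction that would worsen, cannot be derived from the protocol.

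**The case against.** The strongest reply is that the protocol closes most of the route to harm.

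- The repeat exclusions remove most device-related open AEs. This stands, and it limits the size of the problem.
- Visual and neurological findings are judged against the status before each injection. Section 6.4.9 says "Any clinically significant change compared to prior of each device application will be recorded as AE", and section 6.4.8 does the same for vision. The diary captures injection site reactions for 28 days after each treatment. These important categories are therefore largely covered.
- A worsening that makes an AE serious triggers a report within 24 hours (section 14.5.1), and new information on any AE must be documented. The facts may therefore exist in source records or safety reports. But none of this adds a worsening date to the AE fields that section 14.3 lists.
- Rules for placing AEs in a phase may be in the SAP. That is fair, and their absence here is no fault. But an SAP cannot place a worsening by a date that is not among the recorded fields.
- One record at the worst grade is a legitimate choice that avoids counting one condition twice. It suits changes between injections. It does not suit a change of phase and possibly of device.

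A reader might infer more than the text supports. First, that such worsening will be counted in the initial phase, against the comparator for cross-over subjects: no provision assigns AEs to a phase or device by start date, and AEs that start after Visit 9 lie outside the initial phase anyway. Second, that touch-ups suffer the same problem: a touch-up uses the same device in the same phase (section 6.2.2), so neither can be misattributed. Third, that the medical-history rule contradicts the one-record rule: "If such condition, however, deteriorates after the device administration, at any time during the investigation, it should be reported as an AE" concerns conditions not yet held as AEs, so their deterioration is a first record.

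**Conclusion.** The concern holds in a limited form. Followed exactly, section 14.3 loses the date of worsening for an AE that is open at RT1 and worsens after the test-device injection. A stated safety objective needs that date. The conflict between the Glossary and section 14.3 over worsening is a plain inconsistency in the protocol.

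The number of events is probably small and falls mainly on AEs judged not related. Unless causality is changed, those would affect tables of all AEs and of intensity, and would not enter tables of related AEs. Each event in the cross-over group is worth about 0.7 to 1.3 percentage points, on the assumption that comparator subjects make up 25 to 50% of about 300 repeat-treated subjects. The direction of any misplacement depends on an allocation rule that the protocol does not give.

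**What to change.** Make two changes.

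1. Give the Glossary and section 14.3 the same definition of treatment-emergent, stating whether worsening of an existing AE counts.
2. Add to section 14.3: if an AE open at baseline treatment or at RT1 increases in intensity or becomes serious after that injection, it is recorded as a new AE, or as a dated worsening entry linked to the existing record. The entry has its own onset date, intensity, seriousness and causality, and is counted in the phase of that date. Keep the one-record rule for all other changes, including after touch-ups.

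The cost is a short addition to section 14.3 and the CRF completion guide, and a few more AE records. One continuing condition may appear in two phases, so overall tables should count subjects and not records.
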